APPENDIX 1. HYPOGLYCEMIA SYMPTOM QUESTIONNAIRE

Investigative Site Instructions: The subject should complete the Hypoglycemia Symptom Questionnaire at the following time points:

- Just before the IV bolus push dose of insulin is given at the start of the hypoglycemia induction procedure.
- Every time blood is drawn for evaluation of plasma glucose concentration during the induction procedure.
- Just before study drug is administered.
- Every 5±2 minutes after glucagon is administered until 90 minutes post-dosing. (Data will be collected 18 times).
- Every 30±5 minutes (coinciding with plasma glucose measurements) between 90 and 180 minutes post study drug dosing (90 minutes, 120 minutes, and 180 minutes).

Note: If a subject is unable to physically complete the questionnaire, the subject will provide verbal responses, which will be recorded on the questionnaire by study staff. Documentation will be provided on each completed questionnaire as to who completed the form.

Subject Instructions: Please rate the current intensity (severity) of each of the following symptoms on a scale of 1-6, with a minimum score of “1” meaning the symptom was absent and a maximum score of “6” meaning the symptom was severe. For the final question, please answer “yes” or “no.”

Neuroglycopenic Symptoms	Severity Score (1-6)
Dizziness	
Blurred vision	
Difficulty in thinking	
Faintness	
Autonomic Symptoms	Severity Score (1-6)
Sweating	
Tremor	
Palpitations	
Feeling of nervousness	
Overall Assessment of Hypoglycemia	Yes/No
Do you currently feel hypoglycemic?	

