5. Subcutaneous administration of the study drug will be made to the abdomen around the umbilicus as per [Section 9.3.3](#). Clock time of study drug administration will be recorded in the source documents. After study drug injection, the study product will be disposed in a location away from the subject in a manner that maintains the blind. After disposal, the blindfold and headphones will be removed from the subject.
6. Following study drug administration, plasma glucose will be measured every 5 ± 2 minutes through 90 minutes, and every 30 ± 2 minutes thereafter through 180 minutes post-dosing.

7. At 180 minutes post-dosing, the subject will resume insulin therapy and be given a meal as per the standard practice at each site. The subject can be discharged from the clinic if their plasma glucose is >100 mg/dL (> 5.55 mmol/L) and the subject is deemed medically stable.
8. After study drug administration and before 180 minutes post-dosing, if rising glucose levels are observed and if deemed medically necessary, insulin therapy or other medical intervention may be initiated by the Investigator.
 - a. Such intervention is not recommended to occur before 90 minutes post-dosing of study drug.
 - b. Plasma glucose data and assessments of neuroglycopenic symptoms will be censored after the time of intervention, per the statistical analysis plan.
 - c. These interventions (such as insulin, carbohydrates, or a meal) prior to 180 minutes post study drug administration should be captured in the source documents, and further glucose measurements may be performed at the discretion of the Investigator.

Hypoglycemia Symptom Assessments

Subjects will complete a questionnaire regarding severity of hypoglycemia symptoms ([Appendix 1](#)) at the following time points:

1. Just before the IV bolus push dose of insulin is given at the start of the hypoglycemia induction procedure (baseline),
2. Every time blood is drawn for evaluation of plasma glucose concentration during the induction procedure,
3. Just before study drug is administered,
4. Every 5 ± 2 minutes after glucagon is administered until 90 minutes post-dosing, and every 30 minutes (coinciding with plasma glucose measurements) between 90 and 180 minutes post study drug administration.

Local Tolerability and Adverse Events

Local tolerability and AEs will be assessed as follows:

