Overnight fast and glucose monitoring from midnight	—	x	x	—
Hypoglycemia induction and confirmation of steady state	—	x	x	—
Randomization	—	x	—	—
Administration of study medication	—	x	x	—
Hypoglycemia Symptom questionnaire	—	x	x	—
Injection site discomfort scales	—	x	x	—

XSGP-304 Clinical Protocol
G-Pen (glucagon injection)

	Visit 1 Screening	Visit 2 Treatment 1	Visit 3 Treatment 2	Visit 4 Follow-up
Assessment	Day -30 to -3	Check-in: Day -1 Dose 1: Day 1	Target ¹ Check-in: Day 7 Dose 2: Day 8 (Dose 1 + 7-28 days)	Target ¹ Day 10-15 (Dose 2 + 2-7 days)
Draize scales for erythema/edema	—	x	x	—
Venous plasma glucose (PD) ⁴	—	X ⁵	X ⁵	—
Review AE(s)	—	x	x	x
Subject Study Drug Assignment Questionnaire	—	—	x	—

AE=adverse events, BP=blood pressure, ECG= electrocardiogram, HbA1c=glycated hemoglobin, HBV=hepatitis B virus, HCV=hepatitis C virus, HIV=human immunodeficiency virus, PD=pharmacodynamic, (X)=repeat if the visit is occurring outside of the allowed time window (i.e., more than 28 or 30 days have passed since the prior visit), YSI= Yellow Springs Instruments.

¹ Visit 3 should begin (i.e., admission to the CRC between 6 and 8 pm the day before treatment) 7 to 28 days after Visit 2; Visit 4 should occur 2 to 7 days after Visit 3.

² Excluding breast, pelvic and genitourinary exams. Note: height assessment is not required at Visit 4.

³ Temperature, respiration, heart rate and BP (after >5 min seated rest) will be performed at all visits.

Additionally, at visits 2 and 3, heart rate and BP will be repeated immediately prior to, and at 30, 60, 120, and 180 minutes post-dosing, with ±5 minutes for all procedures.

⁴ Via rapid glucose analyzer (YSI 2300 or 2900) before and during hypoglycemia induction, and every 5 minutes post study drug dose through 90 minutes, with ±2 minutes for all collections, and at 120, 150 and 180 minutes with ±5 minutes for collections.

⁵ If plasma glucose is > 350.0 mg/dL (>19.44 mmol/L) upon clinic arrival or if the plasma glucose the morning after the overnight stay is > 270.0 mg/dL (> 15.0 mmol/L) the visit should be rescheduled.

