6.4 General guideline for define the protocol time

Protocol time is needed to find the 30-minute glucose value as well as to generate most of the glucose or hypoglycemia score curves.

Protocol time will be developed based on the following procedures:

- Protocol time zero will be based on either receiving glucagon or decision to dose:
 - Receiving glucagon: T0 = actual time stamp of glucagon injection
 - Decision to dose: T0 = actual time stamp when dose decision is made

- Subsequent protocol times are calculated by the following minutes plus T0 (receiving glucagon):
 - 5, 10,15,20,25,30,35,40,45,50,55,60,65,70,75,80,85,90;
 - 120,150, and180.
- For any continuous (number) variable, the value at the protocol time will be determined by linear interpolation between the two adjacent time points.
- For any categorical (text) variable, the value at the protocol time will be determined using the nearest value:
 - Protocol time 5 – 85: -2 minute to +3 minute;
 - Protocol time 90: -2 minute to 15 minute;
 - Protocol time 120, 150, 180: -15 minute to +15 minute;
 - If multiple values are attributed to a single protocol time, then the last value will be used.

Several analyses will be conducted using both the protocol time based on study drug administration and the one based on decision to dose. These analyses will be noted in each of the corresponding sections.

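### Appendix 1 contradicts itself on the late symptom questionnaires: its 30-minute rule gives 120, 150 and 180 minutes, but its bracketed list repeats 90 and omits 150

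*Protocol*

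**What the plan says.** The last scheduling bullet of the site instructions in Protocol Appendix 1 has two halves. It opens with a frequency, "Every 30±5 minutes (coinciding with plasma glucose measurements", and closes with specific times, "between 90 and 180 minutes post study drug dosing (90 minutes, 120 minutes, and 180 minutes". The bullet before it covers the five-minute series up to 90 minutes and gives its count: "Data will be collected 18 times".

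Three other places bear on the late times:

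- Protocol Section 10.2.1.2, Hypoglycemia Symptom Assessments, asks for the questionnaire "every 30 minutes (coinciding with plasma glucose measurements) between 90 and 180 minutes post study drug administration".
- Protocol Table 5, footnote 4, fixes those late glucose draws "at 120, 150 and 180 minutes with ±5 minutes for collections".
- SAP Section 6.4 builds its late protocol times as "120,150, and180" minutes after injection. For categorical items it sets the window "Protocol time 120, 150, 180: -15 minute to +15 minute". Numeric items are interpolated linearly between adjacent readings.

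The readings feed secondary endpoints 8 (time to relief and to complete resolution of symptoms) and 9 (time to resolution of the overall feeling of hypoglycemia). SAP Sections 5.3.6.2.3 and 6.1 take both from actual assessment times. They also feed the by-timepoint summaries of the average scores (SAP 6.6.3) and of the yes/no question (SAP 5.3.6.2.2).

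**The concern.** The instruction addressed to site staff names explicit times, and a list of times is easily taken as the schedule. Of the three it names, one duplicates an assessment already made and the one that is needed at 150 minutes is absent. Sites that work from the list and sites that work from the frequency rule would collect different data.

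The SAP does not repair the gap. Last-observation-carried-forward applies only to the average scores and only to 90 minutes (SAP 6.6.3), and SAP 7.1 rules out any other imputation. Percentages are based on non-missing values by default (SAP 6.1.1), so a 150-minute percentage for the yes/no question would come only from sites that did collect it. A 150-minute average score would still appear for the other sites, although nothing was measured then. A questionnaire not completed at 150 minutes cannot be recovered later.

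**Working it through.** **Step 1: the plan's own count.** Assessments every 5 minutes from 5 to 90 number 90/5 = 18, which matches Appendix 1. The 90-minute assessment is the 18th, so the 90 in the bracketed list adds nothing.

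**Step 2: the intended late times.** Every 30 minutes after 90 and up to 180 gives 120, 150 and 180. These are the glucose draws in Table 5 footnote 4 and the late points of the SAP 6.4 grid. The bracketed list, without the repeated 90, gives 120 and 180.

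**Step 3: effect on recorded resolution time.** Each true resolution time is carried forward to the next scheduled questionnaire. The subject is assumed still to be resolved at that assessment. Times are nominal minutes after injection.

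| True resolution | Recorded with 120/150/180 | Recorded with 120/180 | Added delay | Maximum lag from true time, with 150 / without 150 |
|---|---|---|---|---|
| after 90, by 120 | 120 | 120 | 0 | 30 / 30 |
| after 120, by 150 | 150 | 180 | 180 − 150 = 30 | 30 / 60 |
| after 150, by 180 | 180 | 180 | 0 | 30 / 30 |

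If resolution is spread evenly within the middle interval (an assumption), the mean lag there is 15 minutes with the 150-minute form and 45 without it. With the ±5-minute windows, the added delay lies between (180 − 5) − (150 + 5) = 20 and (180 + 5) − (150 − 5) = 40 minutes. Endpoints 8 and 9 run from the decision to dose. That adds the same preparation time to both columns, so the added delay does not change.

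**Step 4: the yes/no question at 150 minutes.** The SAP window is 150 ± 15, that is 135 to 165 minutes. The latest 120-minute reading is at 125 and the earliest 180-minute reading is at 175, so neither falls inside and the value is missing. SAP 5.3.6.2.2 analyses this item from the decision to dose. On that clock the conclusion still holds if preparation takes less than 135 − 125 = 10 minutes.

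**Step 5: the average scores at 150 minutes.** Linear interpolation spans 180 − 120 = 60 minutes. With readings on the nominal times, the 150-minute value is simply the midpoint of the 120- and 180-minute scores.

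**The case against.** The strongest reply is that the bullet's opening words, and Section 10.2.1.2, already require a 150-minute questionnaire. A site that follows either collects it, and the eCRF, which is not among the documents, may prompt for it anyway. This stands: the documents show a contradiction, not a loss of data.

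The effect on results is also likely to be slight. Protocol Section 6.4 reports that in XSGP-202 every subject's symptoms had resolved completely within half an hour of injection, and that in XSGP-301 relief peaked at about 30 minutes. The primary endpoint and the symptomatic response are both judged within 30 minutes. Some late data are lost in any case, because insulin or a meal may be given from 90 minutes and neuroglycopenic assessments are then censored. In a crossover a subject is normally assessed at the same site under both treatments, so a site's reading of the list would affect both arms. All of this stands as a limit on importance. One qualification is that the XSGP-301 finding concerns mean scores, whereas complete resolution under SAP 5.3.6.2.3 requires every symptom in the domain to score 1.

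Three stronger readings are tempting, and the documents do not support them:

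- A reader might infer that every visit lacks the 150-minute questionnaire. That would need every site to follow the list over the rule in the same sentence.
- A reader might infer a deliberately thinned schedule. The 30-minute rule, Section 10.2.1.2 and the SAP grid all point to 150 being intended.
- A reader might put a figure on the shift in mean resolution time. That shift is 30 minutes multiplied by the share of visits that resolve after 120 and by 150 minutes at sites using the list. The documents do not give that share, and the earlier studies are compatible with a value at or near zero.

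**Conclusion.** The point holds as an internal inconsistency in a site-facing data-collection instruction. Appendix 1 conflicts with itself, with Section 10.2.1.2 read with Table 5 footnote 4, and with SAP 6.4.

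The consequences are conditional on a site following the bracketed list. They are the missing yes/no answer, the interpolated average scores and the nominal 30-minute added delay set out in the working. The delay applies only to resolution after 120 and by 150 minutes, and it assumes that the subject is still resolved at 180.

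The reach is limited to late readings of secondary endpoints 8 and 9 and the by-timepoint symptom summaries. The primary endpoint and the 30-minute response endpoints are untouched, and no bias between treatments has been shown. The overall effect is probably small and cannot be quantified from the documents. The priority is low, but the correction is worth making because it is so cheap.

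**What to change.** Change the bracketed list in the last scheduling bullet of Appendix 1 to 120, 150 and 180 minutes. This removes the repeated 90 and brings the list into line with the bullet's own frequency, Section 10.2.1.2 and the SAP 6.4 grid. Confirm that the eCRF has a 150-minute questionnaire form.

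The cost is one line of text and one check of the form. Blood is already drawn at 150 minutes, so no visit or procedure is added; subjects at sites that had been using the list would complete one more short questionnaire per treatment visit.

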APPENDIX 2. INJECTION SITE DISCOMFORT ASSESSMENT

Visual Analog Scale (VAS) for Injection Site Discomfort

Investigative Site Instructions: The subject should complete the 100-mm Visual Analog Scale (VAS) for Injection Site Discomfort at 30±5 and 90±5 minutes after injection of study drug, and again at 180±5 minutes after injection of study drug. The 180-minute evaluation after injection of study drug is still required even if glucose monitoring ends at an earlier timepoint. The subject will complete the VAS by drawing a single vertical line through the scale corresponding to the perceived intensity (severity) of discomfort according to the instructions below. The goal is for the subject to report the amount of discomfort, if any, remaining at each time point, as opposed to reporting the transient pain associated with needle insertion.

[figure not shown]
Note: If a subject is unable to physically complete the questionnaire, the subject will indicate the point on the VAS corresponding to their level of discomfort, and study staff will enter a vertical line at that point. Documentation will be provided on each completed questionnaire as to who completed the form.

Please verify the length of the VAS line to be 100-mm before providing it to the subject.

Subject Instructions: Ignoring any pain from insertion of the needle, please draw a single vertical line through the scale below that corresponds to the intensity (severity) of any discomfort you are feeling **right now** at the study drug injection site.

Discomfort could include stinging, burning, tingling, throbbing or pain. The further to the right you make your vertical mark, indicates the more intense discomfort you are feeling.

You should normally draw a straight line across the scale to indicate your current level of discomfort. However, if you are currently feeling no discomfort, you should circle the vertical line on the left end of scale (above the word “no”). If you are currently feeling the worst discomfort possible, you should circle the vertical line on the right end of the scale.

Injection Site Discomfort Description and Duration Questionnaire

Study Personnel Instructions: Question 1a should be completed by the subject at 30±5 minutes after injection of study drug. Any subject reporting discomfort other than “none,” should complete Question 1b at the same time. All subjects should also answer Question 1c at the end of the visit (180 ±5 mins post-injection). The goal is for the subject to report the qualitative nature and duration of discomfort, if any, associated with injection of study drug, ignoring any transient pain associated with needle insertion.

Note: If a subject is unable to physically complete the questionnaire, the subject will provide verbal responses, which will be recorded on the questionnaire by study staff. Documentation will be provided on each completed questionnaire as to who completed the form.

Subject Instructions: Please answer question 1a and, if applicable to you, questions 1b and 1c. In answering these questions, you should ignore any pain from insertion of the needle.

1a. How would you describe any discomfort you felt from the study drug? (Check **all** that apply):

- None (**Please ignore question 1b.**)
- Pain (e.g., throbbing, soreness, muscle ache)
- Itching
- Tingling, twitching or numbness
- Irritation (e.g., burning, stinging)

Other or additional comments: _____

1b. About how long did the discomfort last after the injection? (Check one):

- Less than 1 minute
- 1-2 minutes
- 3-5 minutes
- 6-9 minutes
- at least 10 minutes (**Please complete question 1c before leaving the clinic.**)

1c. In total, how long did the discomfort last after the injection? (Please enter a number below):

_____ Minutes

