1. Subjects will complete a Visual Analog scale (VAS) questionnaire regarding injection site discomfort ([Appendix 2](#)) at 30 ± 5 , 90 ± 5 , and 180 ± 5 minutes after injection of study drug.
2. Subjects will complete an Injection Site Discomfort Description and Duration Questionnaire at 30 ± 5 minutes post-dosing. If discomfort is ongoing at 30 minutes post-dosing, the questionnaire will be updated before the subject leaves the clinic to document the final duration.
3. The Investigator will use the modified Draize scales ([Appendix 3](#)) to assess erythema and edema formation at the injection site at 30 ± 5 , 90 ± 5 , and 180 ± 5 minutes after injection of study drug. If any scores remain > 1 at the 180-minute evaluation, the subject may leave the clinic but will be instructed to contact a study staff member if the condition fails to resolve. The CRC will make every attempt to ensure that the same investigator will assess the injection sites on the subject, during both treatment visits.

Note: Even if the plasma glucose measurements have been stopped after 90 minutes, the Draize scale assessments should continue to 180 minutes post study drug injection.

4. AEs reported by the subject or observed by an Investigator during the visit will be recorded in the eCRF.

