5.3.6.3.7 Local Tolerability

Summaries for tolerability will be presented by treatment and tabulated by scheduled timepoints. Worst post-baseline cases or scores will be determined for each subject and analyzed, which will include all scheduled and unscheduled assessments, if any.

5.3.6.3.7.1 Injection Site Discomfort

The incidence of any injection site discomfort reported by the subject will be analysed descriptively with counts and percentages for all scheduled time points.

- None
- Any injection site discomfort (including 'Other');
- Pain;
- Itching;
- Tingling, twitching or numbness;
- Irritation.

The following descriptive statistics will be provided for all timing variables for subjects reporting at least one injection site discomfort:

- Counts and percentages of time of onset from study drug injection (0-<1 min, 1-2 mins, 3-5 mins, 6-9 mins, >=10 mins);
- Total duration of discomfort will be analysed with descriptive statistics for continuous variables.

5.3.6.3.7.2 Draize Scale (Erythema and Edema)

[figure not shown]
The incidence of erythema and edema will be analysed descriptively with counts and percentages by scheduled timepoints, worst post-baseline score, and by the categories indicated below:

Erythema Formation		Edema Formation	
Description	Score	Description	Score
No erythema	0	No edema	0
Erythema	1-4	Edema	1-4
Very slight erythema: Barely perceptible	1	Very slight edema: Barely perceptible	1
Well defined erythema	2	Well defined edema	2
Moderate erythema	3	Moderate edema: raised approx. 1mm	3
Severe erythema: Beet redness to slight eschar formation	4	Severe edema: raised more than 1mm and beyond exposure area	4

Subject will be counted only once per actual treatment and timepoint and once for worst post-baseline score or erythema/edema occurrence.

5.3.6.3.7.3 VAS

VAS is reported using a 100-mm scale.

VAS scores will be summarized by all timepoints and worst post-baseline score.

Mean VAS scores will be compared between the treatments. Comparison between the treatments will be performed using a mixed model with treatment, period and treatment*period as fixed factors and subject as a random factor. This analysis will be performed on the Safety population.

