7 DATA HANDLING CONVENTIONS

7.1 Missing Data

Unless specified in any of the previous sections, no other missing data will be imputed.

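### The staff instructions and the subject's form disagree on who reports total minutes of injection-site discomfort; if the form is followed, the SAP's mean and median duration cover only discomfort of 10 minutes or more

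*Protocol*

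**What the plan says.** Protocol Appendix 2 contains the Injection Site Discomfort Description and Duration Questionnaire. Item 1a asks what kind of discomfort was felt. Item 1b asks roughly how long it lasted, in five categories from less than 1 minute to at least 10 minutes. Item 1c asks for the total in minutes.

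- The personnel instructions, which put 1c at 180 ±5 minutes, state: "All subjects should also answer Question 1c at the end of the visit".
- The subject's instructions read: "Please answer question 1a and, if applicable to you, questions 1b and 1c". The only prompt to 1c on the form is attached to the top category of 1b: "Please complete question 1c before leaving the clinic".
- Protocol 10.2.1.2 (Local Tolerability and Adverse Events, item 2) has the questionnaire completed at 30 ±5 minutes and adds: "If discomfort is ongoing at 30 minutes post-dosing, the questionnaire will be updated before the subject leaves the clinic to document the final duration".

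SAP 5.3.6.3.7.1 plans descriptive statistics "for all timing variables for subjects reporting at least one injection site discomfort". Two are listed. The first is "Counts and percentages of time of onset from study drug injection", in bins that match the 1b categories. The second is: "Total duration of discomfort will be analysed with descriptive statistics for continuous variables". The SAP does not say how 1b and 1c are to be combined, and SAP 7.1 states: "Unless specified in any of the previous sections, no other missing data will be imputed".

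Discomfort duration is named in secondary endpoint 11 (Protocol 5.3.2, SAP 3.3.2). Protocol 13.5.6 limits its analysis to descriptive statistics.

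**The concern.** Item 1c is the only numeric duration item, so the SAP's continuous summary must come from it. The form is normally completed by the subject. A subject whose discomfort lasted 4 minutes reaches no prompt to 1c and can reasonably leave it blank. Blanks produced this way depend on the outcome itself: the value is missing because the duration was short. The SAP means the summary to cover everyone with discomfort, but it would then cover only the longer episodes.

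The item that does hold the short durations, 1b, is planned for tabulation as time of onset, although the form has no onset question. Read literally, the SAP would report 1b under the wrong name and summarise duration from a selected subset.

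This has some weight because tolerability belongs to the secondary objective, and Protocol 12.2 keeps injection-site reactions out of the adverse event tables unless they need medical intervention. Protocol 6.4 also reports more injection-site pain with the sponsor's glucagon than with a comparator in an earlier Phase 2 study, so local discomfort is a plausible point of difference between the products.

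**Working it through.** **Step 1: the instructions side by side.** The durations are examples.

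| Subject's discomfort | Staff instruction (Appendix 2) | Subject's form (Appendix 2) | Protocol 10.2.1.2 |
|---|---|---|---|
| None | 1c due; 0 or blank not stated | told to skip 1b; no prompt to 1c | no update |
| 4 minutes | 1c due | no prompt to 1c | no update |
| 15 minutes | 1c due | prompted to 1c | no update |
| Still present at 30 minutes | 1c due | prompted to 1c | update with final duration |

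The first two columns conflict for every subject under 10 minutes. The third describes a follow-up step and is compatible with either rule, but it should match whichever is kept.

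**Step 2: direction of the effect.** Among subjects with discomfort, let p be the share under 10 minutes, m_s their mean duration, and m_L the mean in the rest.

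- Mean over all with discomfort = p·m_s + (1 − p)·m_L
- Mean if only those at 10 minutes or more fill 1c = m_L
- Excess = p·(m_L − m_s)

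Since m_s < 10 ≤ m_L, the excess is positive whenever p > 0. Provided 1c agrees with 1b, the restricted median also cannot be below 10 minutes.

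**Step 3: possible size.** The plan gives no expected duration, spread or category share, so there is no figure of its own to reproduce. All inputs here are assumed:

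- 1b shares (<1, 1–2, 3–5, 6–9, ≥10 minutes): 30/30/15/5/20% on drug A and 5/10/15/20/50% on drug B.
- Values for the four lower categories: 0.5, 1.5, 4 and 7.5 minutes.
- Mean of L minutes in the top category, the same on both drugs.

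Contribution of the four lower categories:

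- A: 0.30×0.5 + 0.30×1.5 + 0.15×4 + 0.05×7.5 = 1.575
- B: 0.05×0.5 + 0.10×1.5 + 0.15×4 + 0.20×7.5 = 2.275

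Mean over all with discomfort: A = 1.575 + 0.20·L; B = 2.275 + 0.50·L.

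| L (minutes) | A, all | B, all | Difference, all | A and B, ≥10 only | Difference, ≥10 only |
|---|---|---|---|---|---|
| 15 | 4.6 | 9.8 | 5.2 | 15 and 15 | 0 |
| 30 | 7.6 | 17.3 | 9.7 | 30 and 30 | 0 |
| 60 | 13.6 | 32.3 | 18.7 | 60 and 60 | 0 |

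At L = 30 the overstatement is 30 − 7.575 = 22.4 minutes for A and 30 − 17.275 = 12.7 minutes for B. For A the median over all lies in the 1–2 minute category (cumulative shares 30%, then 60%), whereas the restricted median is at least 10. The zero in the last column follows from giving both drugs the same L.

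**Step 4: what 1b still shows.** In the same illustration, a by-drug table of the 1b categories shows 20% against 50% lasting at least 10 minutes. The difference absent from the restricted mean is visible there, if the table is read as duration.

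**The case against.** The strongest reply is that little is lost. Item 1b records brief discomfort in categories, and the SAP already tabulates those bins by treatment for subjects with discomfort; the onset wording looks like a labelling slip. The VAS at 30, 90 and 180 minutes tracks persistence independently. SAP 6.1.1 already provides the median and minimum, and a minimum near 10 minutes would reveal the truncation. Duration is descriptive, so no test, margin, alpha or power is affected. The problem also disappears if staff enforce their explicit instruction.

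All of that stands, and it limits the point. It does not remove the contradiction within Appendix 2, and the SAP does not settle how a blank 1c is handled or correct the label.

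A reader might go further in three ways that the documents do not support:

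- **Three mutually exclusive rules.** Protocol 10.2.1.2 says to update the form if discomfort is ongoing at 30 minutes. It does not say that only those subjects supply a number.
- **Brief discomfort, or a drug difference in it, is hidden.** It remains in the 1b table, as Step 4 shows.
- **The form is the only record of duration.** It is the only direct record in minutes, but the VAS also shows whether discomfort persists.

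**Conclusion.** The point holds in limited form. Appendix 2 gives two incompatible rules for 1c, and neither document says which governs. If the form's prompt prevails, the continuous summary of total duration is drawn from a subset selected on the outcome, and its mean and median are too long for any drug with discomfort shorter than 10 minutes. The direction follows from the form's wording. The size, and any effect on the contrast between drugs, cannot be derived from the documents; the figures above rest wholly on assumed shares and means.

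The consequence is confined to a descriptive component of secondary endpoint 11. The primary non-inferiority conclusion is untouched. The correction is still worth making because it changes a reported endpoint at almost no cost.

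**What to change.** 1. **Protocol Appendix 2 and 10.2.1.2:** state one rule. Every subject who reports any discomfort in 1a gives a total duration in 1c at 180 minutes. Move the prompt on the form accordingly, and word the 30-minute update to agree. This also settles that subjects reporting no discomfort do not enter a value.
2. **SAP 5.3.6.3.7.1:** relabel the binned table as duration from 1b. Report it by drug for all subjects with discomfort, including the proportion lasting at least 10 minutes, and make it the main duration summary.
3. **Same SAP section:** where 1c is incomplete, give its mean and median only with the number contributing, labelled as restricted to subjects with a 1c value.

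Filling a blank 1c with the 1b category midpoint is optional and works only below 10 minutes. The top category is open-ended, so a blank there cannot be filled this way.

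The cost is a wording change on one form, one protocol sentence and a few SAP lines. For data already collected, items 2 and 3 need nothing new.
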